### 5 RESULTS

#### 5.1 POSTOPERATIVE PAIN INTENSITY

The analysis demonstrated significant main effects of treatment ( $F_{(1,16)} = 5.063$ ,  $p = 0.039$ ) and time ( $F_{(7,112)} = 6.254$ ,  $p < 0.001$ ) on postoperative pain intensity (Table 1). Overall, pain scores were higher in Group A than in Group B ( $2.0 \pm 1.2$  vs.  $1.3 \pm 1.1$ ;  $F_{(1,16)} = 5.063$ ,  $p = 0.039$ ).

[figure not shown]

[figure not shown]
Table 1: Average pain levels on every post-operative day for each group. (\*) indicates statistical differences between control and test groups.

In Group A, pain intensity was significantly higher on postoperative days 1 ( $3.59 \pm 0.59$ ;  $p = 0.014$ ) and 3 ( $3.24 \pm 0.55$ ;  $p = 0.005$ ) compared with day 0 ( $1.35 \pm 0.54$ ). No significant differences were observed between day 0 and the remaining postoperative time points ( $p > 0.05$ ).

[figure not shown]
On the test side (Group B), no significant differences in pain intensity were observed between day 0 and any postoperative evaluation ( $p > 0.05$ ), suggesting that cryotherapy effectively prevented postoperative pain exacerbation.

A significant interaction between treatment and time was also observed ( $F_{(7,112)} = 2.689$ ,  $p = 0.013$ ). Pain intensity was higher on postoperative day 1 (Group A:  $3.59 \pm 0.59$  vs. Group B:  $2.12 \pm 0.42$ ;  $p = 0.017$ ) and day 3 (Group A:  $3.24 \pm 0.55$  vs. Group B:  $1.29 \pm 0.33$ ;  $p = 0.007$ ) in the control group compared with the cryotherapy group.

Postoperative pain was absent in 29.4% of control cases and 44.1% of cryotherapy cases. Mild pain was reported by 50.0% of participants in Group A and 47.8% in Group B, whereas moderate pain occurred in 16.9% and 7.4% of cases, respectively. Severe pain was reported by 3.7% of control cases and 0.7% of cryotherapy cases (Graphics 1 and 2).

Graphic 1: Prevalence of reports of moderate to severe pain (4-10 in visual analogic scale) in the total number of reports of pain (1-10 in visual analogic scale) in the control group after day 2 (last day of analgesic medication).

12

Graphic 2: Prevalence of reports of moderate to severe pain (4-10 in visual analogic scale) in the total number of reports of pain (1-10 in visual analogic scale) in the test group after day 2 (last day of analgesic medication).

When moderate-to-severe pain reports were isolated and compared with the need for rescue medication after suspension of the standard analgesic regimen, 80% of participants in Group A required rescue medication, whereas no participant in Group B required additional analgesia.

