### 4.1 SAMPLE CALCULATION

The sample size was calculated based on a previously published study, which adopted a significance level of 5% ( $p < 0.05$ ), a statistical power of 90%, and a margin of error of 5%, resulting in a required sample size of 40 surgical sites. In the baseline study, pain perception during local anesthesia was compared between acupressure and cryotherapy using a split-mouth design involving 20 patients. Similarly, the present study employed a split-mouth design, with procedures performed on 20 patients, yielding a total of 40 surgical sites.

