#### **4.4 SAMPLE**

The sample selection consisted on patients referred to the Federal University of Rio Grande do Sul's Dentistry School. The selected patients require bilateral extraction of lower third molars under local anesthesia in two different surgical times. There will be no change to the routine care for patients volunteering in the study. The surgical procedures will be performed by the research team responsible for this study. Participants of both sexes, aged 18 to 50 years, were included in the study if they presented an indication for bilateral surgical removal of mandibular third molars in similar positions according to Pell and Gregory classification. Additional inclusion criteria comprised the absence of systemic comorbidities, local conditions free of inflammatory or infectious processes, no history of allergy to the prescribed medications, and no recent or chronic use of antibiotics, anti-inflammatory drugs, corticosteroids, or analgesics. Participants were excluded from the study if they used medications other than those prescribed by the surgeon, failed to provide the required data, belonged to Group A (control) but used postoperative ice packs, or belonged to Group B (test) and did not use ice packs as instructed by the researchers. There were three dropouts due to noncompliance with postoperative recommendations and the use of non-prescribed medication, resulting in 34 procedures performed in 17 patients.

Postoperative consultations were conducted for follow-up, suture removal, and the evaluation and treatment of any potential postoperative complications.

The selection of the control group and experimental groups were determined by a simple randomization in the immediate postoperative period. One surgical site didn't receive cryotherapy (GA), while the other site received cryotherapy with ice (GB).

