#### **4.6 POSTOPERATIVE CARE**

In the immediate postoperative period following the first surgical procedure, the allocation of postoperative care—with or without cryotherapy—was randomized using a simple draw. Allocation was determined by the selection of a folded paper indicating Group A or Group B and was supervised by a third party to ensure allocation concealment. When the first surgical site of a patient was assigned to Group A (control), the contralateral site in the second surgical procedure was assigned to Group B (test), and vice versa.

Group A (control) did not receive postoperative cryotherapy. Group B (test) was instructed to apply standardized ice packs (11 × 8.5 × 1 cm), provided by the research team, positioned diagonally to cover both the mandibular angle and the cheek on the operated side. Cryotherapy was initiated immediately after surgery under surgeon supervision and continued for the first 12 postoperative hours, consisting of 30-minute applications followed by 30-minute intervals (total of 12 applications). During the intervals, patients were instructed to store the ice packs in a freezer until the next application.

All participants received identical pharmacological postoperative instructions (APPENDIX B) for both interventions, including paracetamol 1 g every 6 hours for 3 days and mouth rinses with 0.12% aqueous chlorhexidine digluconate twice daily for 7 days, starting on the day following surgery. In cases of persistent pain, trismus, or edema that significantly interfered with daily activities despite the use of prescribed analgesics, patients were instructed to use rescue medication consisting of codeine 30 mg every 4 hours as needed.

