## APPENDIX C – VAS FOR ASSESSING POSTOPERATIVE

A 10-cm visual analog scale is used to measure the patient's pain during the stipulated periods. It is used postoperatively for each operated side.

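### Section 5.1 reads non-significant changes from day 0 in Group B as prevention of worsening pain, which 17 pairs and no confidence interval cannot support

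*Combined protocol and SAP*

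**What the plan says.** Section 4.8 plans a two-way repeated-measures ANOVA (treatment, time and their interaction) for pain, followed by Fisher's LSD comparisons at the 5% level. It sets no equivalence margin and no rule for concluding that pain did not rise.

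Section 5.1 then states for Group B that "no significant differences in pain intensity were observed between day 0 and any postoperative evaluation" (p > 0.05), and closes the sentence with "suggesting that cryotherapy effectively prevented postoperative pain exacerbation". The text gives no changes, exact p-values or confidence limits for these comparisons.

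The same section reports a treatment main effect (p = 0.039), a treatment-by-time interaction (F(7,112) = 2.689, p = 0.013), and higher pain on the control side on day 1 (3.59 against 2.12, p = 0.017) and day 3 (3.24 against 1.29, p = 0.007).

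On the reference day, Section 4.6 says "Cryotherapy was initiated immediately after surgery under surgeon supervision and continued for the first 12 postoperative hours". Appendix C says of the VAS: "It is used postoperatively for each operated side". Section 4.7 defines day 0 as the day of surgery. On sample size, Section 4.4 records three dropouts from 20 patients, "resulting in 34 procedures performed in 17 patients".

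**The concern.** The sentence treats failure to detect a rise as evidence that none occurred. Under that reasoning, fewer patients or noisier scores make prevention easier to conclude. Prevention of worsening is also a stronger claim than lower pain than control on two named days, and a reader could carry it into practice as a separate benefit.

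The reference point adds to the difficulty. Day 0 was scored after surgery, on the day ice was started. A comparison with day 0 within Group B therefore has no pre-treatment anchor. On its own it also cannot say what would have happened without ice.

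**Working it through.** **1. The plan's own figures.** F(1,16) = 5.063 gives p = 0.0389 and F(7,112) = 2.689 gives p = 0.0130. Both match Section 5.1. The sample size of 40 sites in Section 4.1 cannot be reproduced, because no effect size or SD is stated. The plan therefore offers no design rise against which to judge the within-side tests.

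**2. Power of the within-side test.** Inputs: n = 17 pairs (Section 4.4); 5% level (Section 4.8), taken as two-sided; a rise of d = 0.5 SD of the within-patient change (my benchmark).
- Noncentrality = d × √n = 0.5 × √17 = 2.06.
- On 16 df the critical t is 2.120. Power is 49.1%, so 50.9% of such rises are missed.
- With a pooled error on 112 df the critical t is 1.981. Power is 53.3%, so 46.7% are missed.
- For 80% power on 16 df, d = 0.5 needs 34 pairs. With 17 pairs, 80% power needs d = 0.72.

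If 0.5 SD meant the SD of a single day's scores, power would depend on the day-to-day correlation, which is not stated: 28% at 0, 49% at 0.5, 86% at 0.8.

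**3. What this means in VAS points.** The daily ± values for pain behave as standard errors. For Group A, day 0 to day 1:
- The change is 3.59 − 1.35 = 2.24. With p = 0.014 on 16 df, t = 2.758, so the implied SE is 2.24 / 2.758 = 0.81.
- Taking the printed values as SEs of uncorrelated scores, √(0.59² + 0.54²) = 0.80, which agrees.
- Taking them as SDs, the SE would be 0.80 / √17 = 0.19 and t about 11.5, which does not fit p = 0.014.

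Group B's day-1 SE is then 0.42. Its day-0 mean and spread are not in the readable text (Table 1 is a figure not shown), so I assume a day-0 SE s₀ of 0.20 to 0.54 and a correlation ρ of 0 to 0.5:
- SE of change = √(0.42² + s₀² − 2ρ × 0.42 × s₀) = 0.36 to 0.68.
- Largest observed rise still giving p > 0.05 = 2.12 × SE = 0.77 to 1.45 points.
- Power for a true 1-point rise = 73% down to 28%, so it is missed 27% to 72% of the time.

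As a cross-check, Group A's p-values imply SDs of change of 0.812 × √17 = 3.35 (day 1) and 0.581 × √17 = 2.40 (day 3, from 3.24 − 1.35 = 1.89 and t = 3.252). If Group B were similar, the 95% CI half-width would be 2.12 × 0.581 to 2.12 × 0.812, about 1.2 to 1.7 points.

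**4. Whether the other tests fill the gap.** The interaction is a global test over eight days. It shows that the two profiles differ in shape, not that Group B's is flat. The day 1 and day 3 contrasts compare the sides with each other on one day. None of them gives an upper limit for Group B's change from day 0.

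**The case against.** The strongest reply is that Section 5.1 does not rest on one significant and one non-significant within-side test. The planned interaction test is reported in the next paragraph and is significant, and two direct between-side contrasts agree with it. This stands. A reader might infer from the criticism that the whole pain result comes from reading p > 0.05 as no effect, or that the contrast between Group A's significant rises and Group B's non-significant ones is chance. The documents do not support either inference, because the interaction (p = 0.013) tests the difference in time course directly.

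The half-SD benchmark is mine, and a larger rise would probably have been seen. With SDs of change of 2.40 to 3.35, a rise as large as Group A's on day 1 (2.24 points) would be detected with about 95% to 74% power. So the data do speak against a rise of that size in Group B, but not against a smaller one.

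A reader might also infer that day 0 records pain while ice was being applied. Surgery was in the morning and icing ran for 12 hours, but no section gives the hour of the day-0 rating. All that is established is that it is a postoperative score from the treatment day. If ice had already lowered that score, a later rise would be easier to see, so the choice of reference need not favour the claim. It does leave the change without a pre-treatment meaning.

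Nor can it be said that Group B's pain did rise. If its overall mean of 1.3 averages days 0 to 7, the other seven days average (8 × 1.3 − 2.12) / 7 = 1.18, about 0.9 below day 1. That is indicative only, since its day-0 mean is not in the readable text.

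Finally, the sentence is hedged as a suggestion, and the Abstract and Section 7 claim reduced pain, not prevention of worsening. This limits the consequence, but it does not make the inference valid.

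**Conclusion.** The concern holds for this one sentence. Prevention of worsening is inferred from p > 0.05 with no interval or margin, in a sample that misses a rise of 0.5 SD of the within-patient change about half the time (51% on 16 df, 47% on 112 df). On the VAS, observed rises of roughly 0.8 to 1.4 points could pass as non-significant, given a day-1 SE of 0.42 and the assumed day-0 SE and correlation.

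Lower pain than control on days 1 and 3, and a difference in time course, are unaffected. The correction should be made, but it concerns wording and reporting and does not challenge the main pain comparison.

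**What to change.** In Section 5.1:
- Delete the clause "suggesting that cryotherapy effectively prevented postoperative pain exacerbation".
- Report Group B's mean change from day 0 to each later day with a 95% CI.
- Report the within-patient difference in change (control side minus cryotherapy side) for each day with a 95% CI.
- Note that day 0 is a postoperative score from the day of treatment.
- State only that the time courses differed and that pain was lower on the cryotherapy side on days 1 and 3.

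Results are already reported, so a margin for no worsening cannot now be presented in Section 4.8 as prespecified. Any margin added must be labelled post hoc.

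The cost is a short re-analysis of scores already collected, a few lines of text, and a less favourable statement. No new data are needed.

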## ABSTRACT

Third molar extraction is a common oral surgical procedure often associated with postoperative pain, edema, and functional limitation. Effective postoperative management plays a key role in minimizing morbidity and promoting patient comfort. Strategies such as cryotherapy may contribute to improved recovery and quality of life after surgery. **Objective:** to investigate the effects of cryotherapy on postoperative outcomes (pain intensity, edema, trismus and quality of life) following mandibular third molar extraction. **Materials and Methods:** This study was designed as a randomized split-mouth clinical trial. The sample consisted of 17 patients (34 mandibular third molars with equivalent levels of impaction) who underwent bilateral surgical extraction. The surgical sites were allocated into two groups according to postoperative care: Group A (control side—without cryotherapy) and Group B (test side—with postoperative cryotherapy using ice packs). All intraoperative and postoperative procedures, instructions, and medications were identical for both groups. Patients were evaluated for pain intensity, trismus severity, presence of edema, and quality of life for up to seven days postoperatively (D7). The evaluator was aware of the postoperative intervention applied. Repeated-measures ANOVA was used to analyze each outcome variable, and associations between continuous variables were assessed using Pearson's correlation test. Statistical significance was set at 5% ( $P < 0.05$ ). **Results:** Overall, postoperative pain intensity was lower in patients who received cryotherapy. Group A reported significantly higher pain intensity on postoperative days 1 and 3. No signs of trismus were observed in Group B at the end of the follow-up period, whereas Group A presented restricted mouth opening at D7. Both groups exhibited edema on postoperative day 2 (D2); however, complete regression of edema by D7 was observed only in Group B. Additionally, a significant association between pain intensity and trismus severity was identified in Group A at D7. Quality-of-life assessment revealed significant differences in three questionnaire items favoring Group B, including greater perceived improvement, better mouth opening, and reduced difficulty sleeping. **Conclusion:** The findings suggest that postoperative cryotherapy is effective in reducing pain intensity and trismus following mandibular third molar extraction. Moreover, this physical therapy modality appears to enhance pain tolerance and patients' self-perceived healing.

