## 4.7 STUDY VARIABLES

The outcome variables of this study were postoperative pain, trismus, local edema, and changes in quality of life following mandibular third molar extraction. Postoperative assessments were performed by the research team, consisting of two calibrated surgeons and one supervising professor, on postoperative days 0 (day of surgery), 2, and 7. The following evaluation protocols were applied:

a) Pain assessment: postoperative pain was assessed using a visual analog scale (VAS– APPENDIX C) ranging from 0 to 10, in which 0 represented no pain, 1–3 mild pain, 3.1–6 moderate pain, and 6.1–10 severe pain. Patients completed the scale at home daily until postoperative day 7.

b) Trismus assessment: trismus was evaluated by measuring maximum mouth opening with the patient seated and the tragus–ala plane parallel to the ground. Patients were instructed to open their mouths three consecutive times, and the mean value was recorded. Measurements were obtained as the interincisal distance in millimeters using a measuring tape. In the absence of maxillary or mandibular incisors, the occlusal edges were used as reference points. Measurements were recorded on postoperative days 0, 2, and 7.

c) Edema assessment: facial edema was measured using the method described by Gabka and Matsumura. Three linear facial measurements were obtained in millimeters with a measuring tape: tragus to pogonion, tragus to oral commissure, and lateral canthus to mandibular angle. The mean of these three measurements was calculated to quantify edema. This assessment was performed preoperatively and on postoperative days 2 and 7.

d) Quality of life assessment: quality of life was evaluated using a questionnaire adapted from the OHIP-14 (APPENDIX D), consisting of 14 dichotomous (yes/no) questions addressing daily functional limitations. The questionnaire included items related to chewing and swallowing ability, dietary changes, alterations in taste, mouth opening, voice changes, speech intelligibility, facial appearance, sleep disturbances, and ability to perform work-related activities. The questionnaire was provided to participants on the day of surgery and completed on postoperative days 0, 2, and 7. At the conclusion of the evaluation period following the second intervention, participants also answered the question: “Which intervention did you perceive as resulting in greater postoperative improvement?”

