#### 4.8 STATISTICAL ANALYSIS

Data normality was assessed using the Kolmogorov–Smirnov test. Parametric analyses were applied to compare groups (control side vs. test side) and postoperative time points (from day 0 to day 7). Continuous variables, including pain intensity (VAS scores), maximum mouth opening (mm), and facial edema (mm), were expressed as means  $\pm$  standard deviation (SD).

A two-way repeated-measures analysis of variance (ANOVA), followed by Fisher's least significant difference (LSD) post hoc test, was used to evaluate the main effects of time and treatment, as well as their interaction, for pain intensity, trismus, and edema. Pain reports were also qualitatively analyzed based on the frequency distribution of pain categories (no pain, mild pain, moderate pain, and severe pain) for both groups.

Associations between pain intensity and trismus or edema were assessed using Pearson's correlation coefficient. Trismus and edema were additionally evaluated using the formulas (Baseline – Postoperative) and (Postoperative – Baseline), respectively. Qualitative data related to quality of life were presented as percentages.

All statistical analyses were performed using SPSS software (version 20.0; IBM Corp., Armonk, NY, USA). Statistical significance was set at  $P < 0.05$ .

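### The pain treatment-by-time interaction (p = 0.013) is tested over eight daily scores with no sphericity check or correction, so how firmly the day 1 and day 3 claims can be stated is open

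*Combined protocol and SAP*

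**What the plan says.** Section 4.8 describes the analysis of pain, mouth opening and edema: "A two-way repeated-measures analysis of variance (ANOVA), followed by Fisher's least significant difference (LSD) post hoc test, was used to evaluate". This covers treatment, time and their interaction. Its only named assumption check is a Kolmogorov-Smirnov test of normality. It names no sphericity test, no Greenhouse-Geisser or Huynh-Feldt correction, and no multivariate or mixed-model alternative.

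On pain scoring, section 4.7 says: "Patients completed the scale at home daily until postoperative day 7". Section 4.4 gives the analysed sample: "resulting in 34 procedures performed in 17 patients".

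Section 5.1 then states: "A significant interaction between treatment and time was also observed", with F(7,112) = 2.689, p = 0.013. The between-side differences on day 1 (3.59 vs 2.12, p = 0.017) and day 3 (3.24 vs 1.29, p = 0.007) follow directly. No epsilon or Mauchly result is printed. The abstract carries the day-specific result forward: "Group A reported significantly higher pain intensity on postoperative days 1 and 3".

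**The concern.** A univariate repeated-measures F test over more than two time points has its nominal size only under sphericity. For the interaction, this means that the day-to-day contrasts of the control-minus-cryotherapy differences must all have the same variance. Consecutive daily pain scores rarely behave like this, because neighbouring days tend to be more alike than distant ones. When sphericity fails, the uncorrected test rejects too often.

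The interaction matters because the post hoc method is Fisher's LSD, which does not adjust for multiplicity. Eight days can be compared between sides. A Bonferroni threshold, which is also Holm's first step, would be 0.05/8 = 0.00625, and neither 0.017 nor 0.007 meets it. A significant omnibus interaction is therefore the only multiplicity protection for the day 1 and day 3 statements in the abstract and section 5.1, and for the Discussion's account of pain peaks at 24 and 72 hours. The 1-df overall effect cannot support claims about particular days.

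**Working it through.** **Inputs**
- Patients: 17 (section 4.4). Daily scores per side: 8, day 0 to day 7 (sections 4.7 and 4.8).
- Interaction: F = 2.689 on 7 and 112 df, p = 0.013 (section 5.1).
- Pain time effect: F(7,112) = 6.254. Pain treatment effect: F(1,16) = 5.063, p = 0.039 (section 5.1).
- Mouth-opening interaction: F(2,32) = 4.703, p = 0.016 (section 5.2).
- Epsilon: not in the documents, so it is varied over its whole range.

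**1. Are the printed degrees of freedom the full ones?** Numerator 8 - 1 = 7; error (17 - 1) x (8 - 1) = 112. Both match. The pain-category percentages also fit complete data of 17 x 8 = 136 reports per side: 40 + 68 + 23 + 5 = 136 in Group A and 60 + 65 + 10 + 1 = 136 in Group B.

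**2. Reproduce the stated p.** The upper tail of F at 2.689 on 7 and 112 df is 0.0130, which matches 0.013. A p that still rounds to 0.013 needs epsilon of at least about 0.985, so the p-value itself is uncorrected, not only the printed df.

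**3. Apply the correction.** Refer the same F to 7 x epsilon and 112 x epsilon df.

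| epsilon | df | p |
|---|---|---|
| 1.0 | 7, 112 | 0.013 |
| 0.9 | 6.3, 100.8 | 0.017 |
| 0.8 | 5.6, 89.6 | 0.021 |
| 0.7 | 4.9, 78.4 | 0.028 |
| 0.6 | 4.2, 67.2 | 0.036 |
| 0.5 | 3.5, 56 | 0.047 |
| 0.4 | 2.8, 44.8 | 0.061 |
| 0.3 | 2.1, 33.6 | 0.080 |
| 1/7 (lower bound) | 1, 16 | 0.121 |

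Solving for p = 0.05 gives epsilon = 0.476.

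**4. Which values are plausible?** This step rests on an assumption that is not in the documents: AR(1) correlation rho between the daily side differences, with constant SD. Null trials with n = 17 and 8 days were simulated, 4,000 per setting.

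| rho | true epsilon | p at true epsilon | size of uncorrected 5% test | median sample Greenhouse-Geisser epsilon | p at that median |
|---|---|---|---|---|---|
| 0.3 | 0.88 | 0.017 | 5.8% | 0.63 | 0.033 |
| 0.5 | 0.72 | 0.026 | 6.8% | 0.56 | 0.040 |
| 0.7 | 0.55 | 0.041 | 8.4% | 0.46 | 0.052 |

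A repeat set of runs gave sizes of 6.0%, 7.1% and 9.0%, so about 6-9% overall.

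**5. What does not move?** The pain treatment effect has 1 numerator df, so no correction applies. At their lower bounds (1 and 16 df), the pain time effect gives p = 0.024 and the mouth-opening interaction p = 0.046. Both stay below 0.05 at any epsilon.

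**The case against.** The strongest reply has three parts.

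First, nothing in the documents shows that sphericity failed. This stands. A reader might infer that p = 0.013 is demonstrably too small, but no epsilon, covariance matrix or Mauchly result is given. A reader might also look for evidence in Group A's printed contrasts with day 0. The day 1 difference of 2.24 (p = 0.014) implies SE 0.81, the day 3 difference of 1.89 (p = 0.005) implies SE 0.58, and the variance ratio is about 1.95. That does not help. The interaction depends on contrasts of the side differences, not of Group A alone, and under exact sphericity a ratio this large in either direction occurs in about 14% of samples of 17. The side-difference SEs implied by the day 1 and day 3 p-values, 1.47/2.663 = 0.55 and 1.95/3.092 = 0.63, show no marked heterogeneity, though two values cannot establish sphericity either.

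Second, most plausible scenarios keep the interaction significant. This also largely stands. At the true epsilon, p is below 0.05 for every rho in the table. The Greenhouse-Geisser estimate is biased low with 17 patients and 8 days: its median is about 0.69 even under perfect sphericity (p about 0.029). With Huynh-Feldt, the median p is 0.016, 0.024 and 0.037 at rho 0.3, 0.5 and 0.7. Loss of significance is possible, not predicted.

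Third, section 4.8 does not make the daily comparisons conditional on the interaction, and if they are paired tests with their own error terms, which the unequal SEs fit, epsilon leaves p = 0.017 and p = 0.007 unchanged. Both statements are right. What remains is that unadjusted LSD over eight days has no other multiplicity protection, so the strength of the interaction still governs how firmly those days can be singled out.

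**Conclusion.** The concern holds as a gap in planning and reporting. The interaction p is uncorrected, the assumption behind it is neither checked nor likely for eight serial scores, and a departure from sphericity could only raise p. From the documents alone the corrected p lies between 0.013 and 0.121, passing 0.05 only below epsilon of about 0.476. The narrower figures (size about 6-9%, median Greenhouse-Geisser p about 0.033-0.052) rest on the assumed AR(1) correlation of 0.3-0.7.

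The documents do not show that the interaction loses significance or that the day 1 and day 3 p-values are wrong. The overall pain difference, the pain time effect and the mouth-opening interaction are not threatened on this ground. Severity: should fix.

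**What to change.** In section 4.8, state that every effect involving time with more than one numerator df is reported with a Greenhouse-Geisser correction, or Huynh-Feldt if epsilon exceeds 0.75. In section 5.1, print epsilon and the corrected p beside F.

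If the corrected interaction p is 0.05 or more, present the day 1 and day 3 differences as exploratory in the abstract, section 5.1 and the Discussion, and rest the pain conclusion on the 1-df overall difference (p = 0.039).

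The cost is one sentence in the plan and a few figures that the SPSS repeated-measures output already contains; no new data are needed. The downside is a less favourable stated p, and with 17 patients the Greenhouse-Geisser version errs on the conservative side. The correction does not adjust the eight daily comparisons for multiplicity, so even if the interaction survives, the text should say that those comparisons are unadjusted.
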